	A DLT is defined as the occurrence of any of the following toxic reactions that are considered to be causally related to 3D185 by the PI within the first 35 days after the first dose.
DLT	1) Hematological toxicity:
	• Grade 4 hematologic toxicity;
	• Grade 3 febrile neutropenia (defined as absolute neutrophil count
	$[ANC] < 1,000/mm^3$, with fever, a single temperature of

$> 38.3 \ \mathbb{C}$ or a sustained temperature of $\ge 38 \ \mathbb{C}$ for more than
1 hour) or Grade 3 neutropenia lasts for more than 7 days with or
without drug intervention;
• Grade 3 thrombocytopenia with bleeding or require to platelet transfusion;
2) Non-hematologic toxicity:
 Any Grade ≥ 3 non-hematologic toxicity (except the following conditions that can be controlled by symptomatic treatment within 48 hours: nausea, diarrhea, vomiting, and electrolyte imbalance [except serum phosphorus]; Grade 3 fatigue with duration ≤ 7 days; Grade 3 hypertension that can be self-resolved or controlled by drugs to below 140/90 mmHg or baseline level within 72 hours);
• Serum phosphorus \geq 7 mg/dL that is unable to recover to
< 7 mg/dL within 14 days after phosphorus removal;
• With liver metastasis or baseline transaminase abnormalities:
ALT/AST > 8 \times ULN; without liver metastasis or baseline
transaminase abnormalities: $ALT/AST > 5 \times ULN$;
• 3D185-related AEs that resulted in dose interruption of 3D185 for
\geq 7 days in the first treatment cycle.
If the DLT is clinically recovered to Grade 0-1 within 28 days, the subject can resume the treatment of 3D185. If the subject can resume treatment,
the Investigator may refer to the provisions of Section 6.3 (Precautions and Dose Modifications) for dose modifications to the same dose or reduce by one dose level.

Specification and	3D185 Tablets: specifications: 50 mg/tablet, 30 tablets/bottle
Administration	Administration: Oral (fast), 28 days per treatment cycle
	Subjects must meet all of the following criteria before they can be enrolled:
	1. Age \geq 18 years.

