At the end of the study, the MTD will be inferred based on the DLT data and all safety data observed at all dose levels. The specific MTD estimation method is shown in Section 4.2. The RPTD will be established by taking into consideration of the PK and/or PD profiles and safety data from the dose escalation phase.

The DLT evaluable subject is defined as the subject who received at least 75% of the planned doses of treatment and completed the safety assessment during DLT evaluation period.

During the DLT evaluation period, Subject can withhold 3D185 due to drug-related AEs. If the withholding time is more than 7 days, the AE will be considered as DLT. The subject's dose of 3D185 will not be reduced unless DLT occurs.

4.2. i3+3 Design

Similar to the 3+3 design^[18], the i3+3 is rule-based design, and it is also an interval-based design similar to mTPI^[19]. The specific algorithm of i3+3 design is shown in Appendix 7. Compared to the 3+3 design, the i3+3 design offers greater flexibility (e.g., flexible handling of subject, shedding), higher MTD selection probabilities, and better safety (see Appendix 8 for the comparison results of the simulation trials for 3+3 and i3+3). The target toxicity probability of the MTD in this study is set to pT = 25%, and the equivalence interval (EI) is (16%, 30%). This means

that the MTD should have a toxicity probability near 25% but not below 16% or above 30%. The decision table for the i3+3 design of this study is shown in Figure 1.

[figure not shown]

Figure 1 i3+3 Dose Escalation Decision Table

Note:

This is a decision table for the 3D185 dose-finding study. The target toxicity probability (pT) is 25% and the equivalence interval (EI) is (16%, 30%) for 42 subjects. Each column represents (n) number of DLT evaluable subjects treated at the current dose and each row represents (x) number of subjects with DLTs at the dose level. Each cell in the table provides the dose-assignment recommendation based on the readouts from the corresponding row (x) and column (n). The letters in the decision table represent different dose-assignment recommendations.

The i3+3 dose-escalation phase is expected to enroll 30-42 subjects (maximum sample size will be adjusted according to the first dose entering the i3+3 phase. For details, see Section 4.1). Every 3 subjects as a cohort will be sequentially enrolled.

The specific operation process of i3+3 design is as follows:

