- 4. CBC with differential: whole blood count (absolute value) includes red blood cell count, white blood cell counts, and differential counts (neutrophils, lymphocytes, monocytes, eosinophils, and basophils), platelet count, hemoglobin, and hematocrit. This test should be completed within 7 days prior to the first dose. It is unnecessary to repeat on C0D1 if the subject has no clinical signs and indications. This test should be completed before dosing within 3 days prior to days C1D1, C1D8, C1D15, C1D28, C2D15, C2D28, CxD28, and safety follow-up period. An unscheduled exam can be performed if there are clinical indications.
- 5. Blood biochemistry includes ALT, AST, total bilirubin, BUN (urea nitrogen) or urea, Cr (creatinine), blood glucose, potassium, sodium, chlorine, calcium, phosphate, magnesium, total protein, albumin, albumin/globulin ratio, LDH (lactate dehydrogenase), and ALP (alkaline phosphatase). This test should be completed within 7 days prior to the first dose. It isn't required to repeat on C0D1 if the subject has no clinical signs and indications. This test should be completed before dosing within 3 days prior to days C1D1, C1D8, C1D15, C1D28, C2D15, C2D28, CxD28 and safety follow-up period. Among them, phosphate levels will also be used for PD analysis.
- 6. Coagulation functions include prothrombin time (PT), APTT, and INR. This test should be completed within 7 days prior to the first dose. It isn't required on C0D1 if the subject has no clinical signs and indications. This test should be completed before dosing within 3 days prior to C1D28, every 8 weeks (±7 days) in additional cycles, and safety follow up visit.

- 7. Urinalysis includes specific gravity, pH, white blood cells, red blood cells, proteins, glucose, ketones, and casts. This exam should be completed within 7 days prior to the first dose. If urine protein ++, it is recommended to test 24-hour urine protein quantitation as soon as possible (if within 72 hours). It isn't required on C0D1 if the subject has no clinical signs and indications. This test should be completed before dosing within 3 days prior to days C1D1, C1D8, C1D15, C1D28, C2D15, C2D28, CxD28, and safety follow-up period.

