4.5. Dose Limiting Toxicity (DLT) Definition

A DLT is defined as the occurrence of any of the following toxic reactions that are considered to be causally related to 3D185 by the PI within the first 35 days after the first dose.

- 1. Hematological toxicity:
 - 1. Grade 4 hematologic toxicity;
 - 2. Grade 3 febrile neutropenia (defined as ANC < $1,000/\text{mm}^3$, a single temperature of >

38.3 \mathbb{C} or a sustained temperature of \geq 38 °C for more than 1 hour) or Grade 3 neutropenia

lasts for more than 7 days with or without drug intervention;

3. Grade 3 thrombocytopenia with bleeding or require to platelet transfusion;

- 2. Non-hematologic toxicity:
 - 4. Any Grade ≥ 3 non-hematologic toxicity (except the following conditions that can be controlled by symptomatic treatment within 48 hours: nausea, diarrhea, vomiting, and electrolyte imbalance [except serum phosphorus]; Grade 3 fatigue with duration ≤ 7 days; Grade 3 hypertension that can be self-resolved or controlled by drugs to below 140/90 mmHg or baseline level within 72 hours);
 - 5. Serum phosphorus ≥7 mg/dL that is unable to recover to < 7 mg/dL within 14 days after phosphorus removal;
 - 6. With liver metastasis or baseline transaminase abnormalities: ALT/AST > 8 × ULN; without liver metastasis or baseline transaminase abnormalities: ALT/AST > 5 × ULN ;
 - 7. 3D185-related AEs that resulted in dose interruption of 3D185 for \geq 7 days in the first treatment cycle.

If the DLT is clinically recovered to Grade 0-1 within 28 days, the subject can resume the treatment of 3D185. If the subject can resume treatment, the Investigator may refer to the provisions of Section 6.3 (Precautions and Dose Modifications) for dose modifications to the same dose or reduce by one dose level.

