> 9.0 mg/dL (> 2.9 mmol/L)	Withhold ^a 3D185 treatment until the serum phosphate level returns to $< 5.5 \text{ mg/dL}$. Resume at the next lower dose level in case of serum phosphate level returns to below 5.5 mg/dL within 7 days. Reduce by two dose levels if it takes 7~28 days to return to below 5.5 mg/dL despite adequate medical management. A second dose reduction may be implemented if needed or clinically indicated for persistent ^b hyperphosphatemia (\geq 7 mg/dL) at every cycle.	Restriction of phosphate intake to 600 – 800 mg/day. Sevelamer up to 1,600 mg 3 times a day with food AND Acetazolamide 250 mg 2 or 3 times a day only until serum phosphate level returns to < 5.5 mg/dL.
> 10.0 mg/dL (> 3.2 mmol/L) or significant alteration in baseline renal function OR Grade 2 hypercalcemia concurrent with hyperphosphatemia	3D185 should be discontinued permanently. (In situations where the subject is having clinical benefit and the investigator and the sponsor's medical monitor agree that re-starting drug is in the best interest of the subject, the drug may be re- introduced at two dose levels lower if appropriate ^c . Follow other recommendations described above.)	Medical management as clinically appropriate.

Note: These are general guidelines that are based on emerging data of other selective FGFR inhibitors and and/or the experts in the field. The treating physicians must use clinical judgment and local standard of care to decide the best way to manage phosphate elevation. If Sevelamer hydrochloride (renagel) is not available, use of other phosphate binders (non-calcium containing) based on the local standard is recommended, including Sevelamer carbonate (Renvela) or lanthanum carbonate (Fosrenol). a. Drug interruptions for hyperphosphatemia suggested to be 7 days duration

b. Persistent hyperphosphatemia is considered to be more than 1 sequential phosphate value of \geq 7 mg/dL c. If a subject has been deriving benefit from treatment, and the investigator can demonstrate that reintroduction of study drug is in the best interest of the subject considering the terminal nature of the disease, the drug may be re-introduced at a lower dose and/or intensity if the medical monitor is in

Serum Phosphate Level	Dose Modification	Medical Management					

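### The dosing-interruption DLT starts at 7 days in the DLT definition but at more than 7 days elsewhere, so a drug-related hold of exactly 7 days has no settled classification

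*Protocol*

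**What the plan says.** The protocol states the interruption rule five times, in two forms.

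- **More than 7 days, in the DLT evaluation period.** Section 4.1 has "If the withholding time is more than 7 days, the AE will be considered as DLT". The synopsis (Study Design and Plan) and Section 6.3.2 carry the same sentence.
- **7 days or more, in the first treatment cycle.** Section 4.5 lists 3D185-related "AEs that resulted in dose interruption of 3D185 for \geq 7 days in the first treatment cycle" among the DLT criteria. The DLT entry of the synopsis gives the same limit.

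Three other provisions bear on the point:

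- A DLT-evaluable subject is one who "received at least 75% of the planned doses of treatment and completed the safety assessment during DLT evaluation period" (Section 4.1).
- During the DLT period the "dose of 3D185 will not be reduced unless DLT occurs" (Section 4.1; the synopsis and Section 6.3.2 agree).
- Footnote a to Table 4 (Section 6.3.1) reads "Drug interruptions for hyperphosphatemia suggested to be 7 days duration".

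**The concern.** The two forms disagree about a hold of exactly 7 days, and nothing in the protocol ranks one above the other. DLT frequency is part of the primary endpoint. The DLT count among evaluable subjects is the input to the i3+3 decision table, and the DLT data feed the isotonic regression that selects the MTD (Section 4.2). Two sites could report different DLT counts from identical data. The label also acts on the subject, because it decides whether the dose may be reduced within the DLT period.

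The case is foreseeable. Section 6.3.1 names hyperphosphatemia as a possible toxicity from the preclinical results and as common in the drug class, and the protocol itself suggests 7-day interruptions for it.

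**Working it through.** The plan has no figure of its own to reproduce here. The check sets the texts side by side and then follows one disputed subject through the protocol's rules.

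**1. Classification by length of hold** (related AE, within Cycle 1, no other DLT criterion met)

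| Hold | Synopsis DLT entry, 4.5 | Synopsis design text, 4.1, 6.3.2 |
|---|---|---|
| 6 days or fewer | not a DLT | not a DLT |
| exactly 7 days | DLT | not made a DLT by this rule |
| 8 days or more | DLT | DLT |

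Only the middle row conflicts. The windows differ too, but no dose is planned between the single dose and C1D1, so the window difference alone has little practical effect.

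**2. Can hold length alone decide?** Yes, for phosphate above 7 and up to 9 mg/dL. Section 8.5.1 grades this as Grade 2, so the Grade 3 criterion is not met. The phosphorus criterion in Section 4.5 requires failure to fall below 7 mg/dL within 14 days. Table 4 calls for a hold at 7.0–9.0 mg/dL. Chemistry, including phosphate, is due at C1D8 and C1D15 (Table 3, note 5: "This test should be completed before dosing within 3 days prior to days C1D1, C1D8, C1D15, C1D28"). On nominal days, a hold started on the first result and released on the second omits 15 − 8 = 7 daily doses. With the −3/+0 day windows the draws can be 12 − 8 = 4 to 15 − 5 = 10 days apart.

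**3. Is the subject evaluable?** Planned doses in the DLT period are 1 + 28 = 29, or 28 if only Cycle 1 counts. For a hold wholly within Cycle 1 and no other missed dose:

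| Doses missed | of 29 | of 28 | At least 75%? |
|---|---|---|---|
| 6 | 23/29 = 79.3% | 22/28 = 78.6% | yes |
| 7 | 22/29 = 75.9% | 21/28 = 75.0% | yes |
| 8 | 21/29 = 72.4% | 20/28 = 71.4% | no |

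The subject with seven missed doses stays in the denominator n, and only the DLT count x is in dispute.

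**4. Effect on the recommendation.** Appendix 7 with equivalence interval (16%, 30%) at n = 3:

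- x = 0: 0 is below 0.16, so E.
- x = 1: 0.333 is above 0.30 and 0/3 is below 0.16, so S.
- x = 2: 0.667 is above 0.30 and 0.333 is not below 0.16, so D.
- x = 3: D.

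Let the other two evaluable subjects have independent DLT probability p. Relabelling the disputed subject as a DLT gives:

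| p | E to S: (1 − p)² | S to D: 2p(1 − p) | Either: 1 − p² |
|---|---|---|---|
| 0.16 | 70.6% | 26.9% | 97.4% |
| 0.25 | 56.3% | 37.5% | 93.8% |
| 0.30 | 49.0% | 42.0% | 91.0% |

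In the remaining p² the letter is D both ways. Figure 1 is not visible in the text, so its DU cells are not used.

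**5. Edge doses.** At an intermediate dose both changes alter the next dose. Under Section 4.2, D at the lowest dose keeps the current dose, so only the E-to-S column matters there. At the highest dose E keeps the current dose, so only the S-to-D column matters.

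**6. Larger n.** At n = 6 the same two steps (0 to 1, 1 to 2) change the letter. At n = 9 the steps are 1 to 2 and 2 to 3. No probability is given, since it depends on how the dose was reached.

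**The case against.** The strongest reply is that the texts can be read together. Section 4.5 is headed as the definition and opens "A DLT is defined as the occurrence of any of the following toxic reactions", which a 7-day interruption satisfies. The other sentence gives a sufficient condition and never says that 7 days is not a DLT. This reading is available, but the protocol does not adopt it. Section 6.3.2 is the operative instruction on withholding, and a reader told there that more than 7 days makes a DLT will naturally infer that 7 days does not.

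Second, the protocol does not define how withheld days are counted. Counted from dose to dose, a last dose on C1D7 and the next on C1D15 are 8 days apart, which exceeds both limits. That stands against the worked example. It moves the boundary without removing it: six omitted doses then give a gap of exactly 7 days, and that subject is evaluable at 78.6% or 79.3%.

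Third, the affected case is narrow, and this stands. The hold must be exactly 7 days and related, with no other criterion met. At seven missed doses, one more makes the subject non-evaluable. Phosphate above 9 mg/dL is Grade 3 and, since phosphorus is excluded from the electrolyte exception, is already a DLT. The body of Table 4 ends a hold by phosphate level, and its footnote only suggests 7 days.

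Fourth, the SMC includes the principal investigators of all sites and the sponsor's medical monitor, reviews all safety data, and only takes the i3+3 recommendation into consideration. This limits the effect on dose assignment. It does not settle which count is reported for the primary endpoint or used to select the MTD. The consequence for dose reduction is also modest in the phosphate example, because Table 4's default at 7.0–9.0 mg/dL is to resume at the same dose.

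**Conclusion.** The contradiction is real: one DLT criterion has two thresholds and two windows, with no rule of precedence. It matters only for an evaluable subject with a related hold of exactly 7 days and no other DLT criterion met. Given such a subject in a first readout of three at an intermediate dose, the recommended next dose changes in about 97, 94 or 91% of readouts for DLT rates of 16, 25 or 30% in the other two. At the lowest dose the share is 70.6, 56.3 or 49.0%, and at the highest 26.9, 37.5 or 42.0%.

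These figures are conditional on that subject existing, on independence of the other two, and on Appendix 7 as written. The lowest-dose figures also need three subjects at 25 mg as a first readout, which happens only if the accelerated-titration subject there has a Grade 2 or higher related AE. The documents give no frequency of 7-day holds, so no overall error rate is claimed. The point should be fixed because it concerns a definition in the primary endpoint and is cheap to repair.

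**What to change.** Reconcile the five statements (synopsis design text, synopsis DLT entry, Sections 4.1, 4.5 and 6.3.2) to one threshold and one window, chosen by the sponsor and worded identically. State whether withheld days are counted as omitted doses or as the interval between doses. Which threshold is right is a clinical decision and is not judged here.

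Then check the chosen wording against the 75% evaluability rule. A hold of eight omitted doses within Cycle 1 leaves 72.4% or 71.4%. Read literally, a subject whose DLT is that hold drops out of the evaluable set, since the rule states no exception for subjects with a DLT.

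The cost is protocol wording only, with no change to sample size, visits or data collection.

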4. STUDY DESIGN AND PLAN

4.1. Overall Plan

This is an open-label, global multicenter, dose-escalation phase 1 study of 3D185 monotherapy in subjects with advanced solid tumors.

The starting dose in this dose-escalation study is 25 mg, and the preset 7 dose-escalation cohorts are 25 mg, 50 mg, 100 mg, 150 mg, 200 mg, 250 mg, and 300 mg, respectively. This study adopts a combination of accelerated titration and i3+3^[1] for dose escalation. All subjects in each cohort will receive a single oral dose of 3D185, followed by a 7-day washout period (i.e. single-dose PK study period). Then, subjects will receive consecutive daily doses (QD, 28 days/cycle) until disease progression, death, unacceptable toxicity, or withdraw of informed consent, whichever comes first. The DLT evaluation period includes the single-dose PK study period and the first treatment cycle (within 35 days after the first dose). The enrolled subjects will be sequentially assigned to the planned dose cohorts according to the protocol, and receive 3D185 treatment to observe the occurrence of DLT:

Accelerated titration dose-escalation phase: One subject is to be enrolled sequentially to 25 mg and 50 mg cohorts, respectively. If no Grade ≥ 2 drug-related AE occurs during DLT evaluation period, the study will escalate to the next dose level. Otherwise, 2 additional subjects will be enrolled, and the subsequent study will convert to i3+3 dose-escalation design from this dose cohort.

In the accelerated titration phase, a subject may be replaced if he/she 1) does not reach to 75% of the total planned dose; 2) discontinued investigational product due to non-DLT reasons during the DLT evaluation period.

i3+3 dose-escalation phase: Starting at 100 mg cohort, 3 subjects are to be enrolled initially at each subsequent dose cohorts in accordance to i3+3 dose-escalation design. Each dose cohort should recruit at least one subject from each country after sites in both countries are activated. If a cohort requires ≥ 6 subjects, it must enroll at least 1 subject from each country and efforts will be made to ensure number of subjects enrolled from each country is similar.

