- ♦ Three subjects will be enrolled in a cohort to receive the planned dose of 3D185. When i3+3 dose-escalation phase starts, if there is no Grade ≥ 2 drug-related AE occurs during the accelerated titration phase, the subjects in the first cohort in this phase will receive 100 mg 3D185. Otherwise, one of the subjects from the accelerated titration dose-escalation cohort will be enrolled in the first cohort of the i3+3 phase. And 2 additional subjects will be enrolled in this first cohort.
- After the three subjects in each cohort complete the DLT evaluation, the dose-assignment recommendation for the next cohort will be determined according to the decision table (Figure 1) by using the safety data from the DLT evaluable subjects.
 - 1) In Figure 1, "E" stands for escalating to the next higher dose; "S" stands for staying at the current dose; "D" stands for de-escalating to the previous lower dose.
 - 2) "DU" indicates that the toxicity at the current dose level is too high. Thence, it stands for de-escalating to the previous lower dose and marking the current and the higher doses as unacceptable so that it will never be used again in the remainder of the trial to avoid other subjects receiving treatment at these doses to ensure their safety. If the current dose is the lowest dose and the dose-assignment recommendation is "DU", the study should be terminated to ensure the safety and no dose level will be selected as the MTD.
 - 3) If the current dose is the lowest dose and the dose-assignment recommendation is "D", the study will continue to enroll new subjects at the current dose. Once the dose-assignment recommendation is "DU", the study should be terminated to ensure safety.
 - 4) If the current dose is the highest dose and the dose-assignment recommendation is "E", the study will continue to enroll new subjects at the current dose.
 - 5) Figure 1 is still applicable in the situation of subjects who have withdrawn due to some reason or more than 3 subjects enrolled in the current dose cohort. For example, if one of three enrolled subjects have withdrawn from the study due to some reasons, the i3+3 design will always appropriate to make a decision based on the data from the remaining 2 DLT evaluable subjects.

 \diamond Repeat the steps of 1) and 2) until the maximum sample size is reached.

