9.2.1. Analysis Population

Full Analysis Set (FAS)

The FAS will include all subjects who received 3D185 treatment in this study. The FAS will be the primary population for evaluating all efficacy, safety and subject characteristics.

DLT Analysis Set (DLT set)

The DLT set will include all subjects who received at least \geq 75% of the planned doses of treatment and completed the safety assessment during DLT evaluation period. The frequency and severity of DLT will be analyzed.

PK Analysis Set (PKS)

The PK set will include subjects who have received at least one dose and have at least once evaluable PK sample collection after administration.

PD Analysis Set (PD set)

The PD set will include subjects who have received at least one dose and have at least once serum phosphate level measurement (serum biochemistry) after administration.

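### The interruption DLT has two limits (at least 7 days, more than 7 days), and the 75%-of-doses rule, with no DLT exception, can remove a DLT subject from the i3+3 count

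*Protocol*

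**What the plan says.** **Interruption limit.** Section 4.1 states: "If the withholding time is more than 7 days, the AE will be considered as DLT". The synopsis design text and Section 6.3.2 say the same. Section 4.5 item 7 instead lists "3D185-related AEs that resulted in dose interruption of 3D185 for" 7 days or longer in Cycle 1, and the synopsis DLT list matches it. Section 6.3.1, Table 4, requires a hold at serum phosphate of 7.0 mg/dL and above, and note a adds: "Drug interruptions for hyperphosphatemia suggested to be 7 days duration".

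**Who is counted.** Section 4.1 and the synopsis: "The DLT evaluable subject is defined as the subject who received at least 75% of the planned doses of treatment", with completion of the safety assessment as a second condition. The DLT set in Section 9.2.1 and the synopsis again requires at least 75% "of the planned doses of treatment and completed the safety assessment during DLT evaluation period". Section 4.2 sets the next cohort's recommendation "according to the decision table (Figure 1) by using the safety data from the DLT evaluable subjects". Its item 5 gives the example of three enrolled and one withdrawn, where the design is used "to make a decision based on the data from the remaining 2 DLT evaluable subjects".

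**Other counting text.** Appendix 7 defines n as the patients treated at the dose and x as those with DLTs there. The Figure 1 note limits n to evaluable subjects but does not limit x.

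**Exceptions that do exist.** Section 5.4.1 treats a subject who stopped because of a DLT as having completed the study. In accelerated titration, Section 4.1 says "a subject may be replaced if he/she 1) does not reach to 75% of the total planned dose", without excluding DLT subjects. The second replacement criterion there is limited to stopping for reasons other than a DLT.

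**The concern.** DLT frequency is part of the primary endpoint, and the MTD is a primary objective. Every i3+3 recommendation depends on x (subjects with DLTs) and n (subjects counted), so both must be fixed before the first cohort is read.

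As it stands, x for a 7-day hold depends on which section is open. That case is foreseeable. Hyperphosphatemia is an expected toxicity of the class, Table 4 calls for holds, and 7 days is the length it suggests.

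The second problem is larger. Toxicity that interrupts or ends dosing is what takes a subject below 75% of planned doses. A rule meant to set aside subjects with too little exposure to be informative therefore also sets aside subjects whose low exposure was caused by a DLT. If x and n both lose that subject, the table can recommend a higher dose after a real DLT.

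**Working it through.** **The plan's own interval.** Section 4.2 and Appendix 8 give a target of 25%, ε1 = 0.09 and ε2 = 0.05. Then 0.25 − 0.09 = 0.16 and 0.25 + 0.05 = 0.30, which reproduces the stated interval (16%, 30%).

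**Doses in the DLT window (Section 4.1).** One single dose plus 28 daily doses = 29. The share received is (N − missed)/N and must be at least 0.75. With N = 29, 0.75 × 29 = 21.75, so 22 doses are needed.

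| Doses missed | N = 29 | N = 28 (Cycle 1 only) | Evaluable |
|---|---|---|---|
| 7 | 22/29 = 75.9% | 21/28 = 75.0% | yes |
| 8 | 21/29 = 72.4% | 20/28 = 71.4% | no |

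The cut falls at 8 missed doses under either denominator. For an early stop, a last dose on C1D20 gives 21/29 = 72.4% (out). A last dose on C1D21 gives 22/29 = 75.9% (in).

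**Decision rule (Appendix 7).** If x/n is below 0.16, escalate (E). If it is inside the interval, stay (S). If it is above 0.30, stay when (x − 1)/n is below 0.16, otherwise de-escalate (D).

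*Limit conflict.* First cohort of three, one subject with a hold of exactly 7 days, no other DLT:
- At least 7 days: 1/3 = 0.333 > 0.30 and 0/3 < 0.16, so S.
- More than 7 days: 0/3 = 0 < 0.16, so E.

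*Evaluability.* First cohort of three; a long-hold subject is one with a DLT who missed 8 or more doses:

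| Situation | Appendix 7 (all treated) | Section 4.2 (evaluable only) |
|---|---|---|
| One long-hold DLT, no other | 1/3 → S | 0/2 → E |
| Two long-hold DLTs, no other | 2/3 = 0.667, and 1/3 is not below 0.16 → D | 0/1 → E |
| One long-hold DLT plus one evaluable DLT | 2/3 → D | 1/2 = 0.50, and 0/2 < 0.16 → S |

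With six treated, 1/6 = 0.167 (S) becomes 0/5 (E), and 2/6 = 0.333 with 1/6 not below 0.16 (D) becomes 1/5 = 0.20 (S).

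The Figure 1 note, read literally, is a third rule: all DLTs in x, evaluable subjects in n. The first situation is then 1/2, which is S. The second is x = 2 with n = 1, which is not a possible cell.

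**Direction.** Removing one DLT subject changes x/n to (x − 1)/(n − 1), which is never larger than x/n when x ≤ n. Some decisions do not change: 3/3 and 2/2 are both D. None of the cases above moves towards de-escalation.

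Figure 1 is not reproduced in the text at hand, so D at 2/3 might be DU in the table. The contrast with S or E is unaffected.

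**The case against.** **The evaluable-only count is not the only written rule.** Appendix 7 counts everyone treated, and the Figure 1 note leaves x unrestricted. This stands. A reader might infer that the protocol drops these DLTs everywhere. It does not: the exclusion follows from Sections 4.2 and 9.2.1. But this replaces a settled error with a conflict between counting rules, and Section 4.2 is the operating procedure.

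**Not every interruption DLT is lost under the more-than-7-days wording.** A reader might infer that item 7 could then never add to x. The documents do not support that. Measured from last dose to next dose, 7 missed doses make an 8-day gap, which exceeds 7 days and is still evaluable. A hold starting on C1D22 or later misses at most 7 doses in the window, so it stays evaluable even if it runs on.

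**The safety monitoring committee sees all treated subjects.** Section 4.1 has it review non-evaluable subjects too, with enrollment paused and the table only one input, and MTD selection draws on all safety data. A dropped DLT would be visible. This softens the consequence, but discretion does not define x and n.

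**Grade 4 events need not end treatment.** Section 6.3.3 requires permanent discontinuation but allows re-introduction. Table 6 allows withholding as the initial action, and Section 4.5 allows resumption after recovery to Grade 0-1 within 28 days. So an early stop is possible rather than certain. A subject who misses 8 doses in the window is still excluded.

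**Accelerated titration is largely covered.** A drug-related Grade 2 or higher event converts that dose to i3+3, and Section 4.2 carries the subject into its first cohort. Replacement is also optional. Little remains of the point there.

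**Conclusion.** Two defects stand.

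First, the interruption limit contradicts itself across five places. This affects only holds of exactly 7 days, where it separates Stay from Escalate in a first cohort of three with no other DLT. Alone it would be a small correction.

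Second, and more important, the evaluability rule has no DLT exception. Under Sections 4.2 and 9.2.1, a DLT subject who misses 8 or more planned doses in the window is excluded, whereas Appendix 7 counts that subject. One such subject turns 1/3 (Stay) into 0/2 (Escalate), and two turn 2/3 (De-escalate) into 0/1 (Escalate). The exception in Section 5.4.1 suggests that its absence here is an oversight.

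The results rest on the Appendix 7 algorithm, the stated interval, 29 or 28 planned doses, and holds counted in missed daily doses within Cycle 1. A reader might go further and infer that the final MTD will be too high. The documents do not support a figure for that: they give no rate of holds, and the DU cut-offs are in a figure not reproduced in the text at hand. Nor do they show which limit is right. Because the counts steer dose assignment for later subjects, both should be corrected.

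**What to change.** (a) State in the synopsis and Sections 4.1, 4.2 and 9.2.1 that a subject with a DLT in the DLT evaluation period is DLT-evaluable whatever share of planned doses was taken and whether or not the remaining assessments were completed. Define n and x in Appendix 7 and the Figure 1 note the same way.

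(b) Use one interruption limit in both synopsis places and Sections 4.1, 4.5 and 6.3.2, counted in missed daily doses. The sponsor should choose it. At least 7 days keeps the Section 4.5 definition, but the phosphate hold that Table 4 suggests would then itself be a DLT. More than 7 days avoids that but is less cautious, and it needs (a) alongside it, since 8 missed doses in the window already make the subject non-evaluable.

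(c) Optionally, limit the 75% replacement criterion in accelerated titration to subjects without a DLT.

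The cost is amendment wording, with no added procedures and no change to the planned maximum sample size. The downside is slower escalation than under the literal evaluable-only rule, which is the intended effect.
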